4. WRITTEN INFORMED CONSENT; ENROLLMENT AND RANDOMIZATION

Written Informed Consent and Enrollment:

Patients who are eligible and interested will be invited to an in-person, group-based, "Initial Visit," at which the study will be fully described, written informed consent will be obtained (Informed Consent document uploaded with this initial Study Application), and baseline self-report and clinical assessments will be performed. Approximate duration for this visit is 3 hours.

Randomization:

The study will apply a block randomization scheme, which will be computer-generated by the trial statistical consultant and administered by designated research staff. The study statistician will place assignments into sealed envelopes labeled with participant ID numbers. At the conclusion of the Initial Visit, the Project Manager will unveil group assignment. Laboratory staff who perform the clinical assays (primary study outcomes), data analysts, and research staff (with the exception of the Project Manager who will conduct randomization) will be blinded to group assignment.

At the conclusion of the Initial Visit, participants will be randomized to DD or DD-Me, delivered through automated text message, or telephonic communication, meet study staff (nurse, medical assistant [MA]), and receive training on intervention devices. All participants will continue to receive standard care at the clinic. Month-6 and month-12 assessments will be conducted at the same site. DD and DD-Me will be delivered between baseline and month-6 assessments, and are both intended to enhance the self-management support component of the Chronic Care Model (CCM).

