7. STUDY SCHEDULE

Intervention assignments are described above. The follow-up periods at months 6 and 12 were chosen to assess immediate and longer-term impact of the intervention, respectively.

- *~1 week prior to Baseline Visit*: EHR Screening, Telephone Screening
- *Baseline Visit*: Informed Consent, Randomization, Brief diabetes education session to be delivered, Labs, blood pressure (BP) and anthropometric data to be obtained, Self-report surveys to be collected
- *Months 1-6*: Delivery of text messages all groups, automated (group 2) or telephonic feedback (group 3)
- *Month 6*: Labs, BP and anthropometric data to be obtained, Self-report surveys to be collected
- *Month12*: Labs, BP and anthropometric data to be obtained, Self-report surveys to be collected

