This study will enroll $N = 414$ men and women allocated equally to the three groups. RMASS2 was used to estimate the sample size needed to detect statistically significant differences between any of the 3 groups: (a) Dulce Digital, (b) DD-Me (automated delivery), and (c) DD-Me (telephonic MA delivery). For HbA1c, the study primary outcome, a clinically meaningful change of 0.5% with a 1.3% standard deviation was used to determine power. To transform this estimate into an effect size ($d=.33$), standard deviations (SD) from prior studies in the same and similar populations were used. To determine the minimum sample size necessary, assumptions included: (1) An alpha level of .05 and a power level of .80; (2) a missing data rate of 15% at each time-point or a 30% missing data rate overall, and (3) a stationary autoregressive structure (lag 1) for the variance-covariance matrix of the repeated measures, using an autocorrelation value of .45. Given these assumptions and the estimated effect size from above, 414 participants are needed at baseline (i.e., $n=138$ in each of the 3 groups). Although power analyses used HbA1c as the primary outcome, $N=414$ at baseline is adequate to detect a small-to-medium effect size for all physiological and patient-reported outcomes, given a missing data rate of 30% over the course of the study. Allowing for up to 30% attrition, the minimum number of participants required to be retained at 12-months follow-up to ensure adequate power for statistical analysis is 290.

Analytic Plan

All analytic strategies will follow published standards, including intent to treat principles. Preliminary data screening and cleaning will require examination of distributions for normality, outliers, and missing data patterns at both the uni- and multi-variate level. Preliminary inferential statistical testing and effect size consultation will be used to determine if random assignment has resulted in statistical equivalence between groups. Significant covariates will be added to adjust for nonequivalence. Or variables related to missing data Multilevel models using full information maximum likelihood estimation will be conducted to examine changes in the target outcomes for each Aim. Analyses will include the between-subjects factor treatment group and the within-subjects factor time. The cross-level group by time interaction effect will be of primary interest. Within groups changes will also be examined to evaluate

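### The primary HbA1c model should fix its handling of baseline in advance; as ordinarily read it gives up about 24% (month 6) and 32% (month 12) of the available precision

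*Combined protocol and SAP*

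**What the plan says.** The SAP's Analytic Plan describes multilevel models fitted by full-information maximum likelihood: "Analyses will include the between-subjects factor treatment group and the within-subjects factor time". It continues: "The cross-level group by time interaction effect will be of primary interest".

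The only provision for covariates is conditional: "Preliminary inferential statistical testing and effect size consultation will be used to determine if random assignment has resulted in statistical equivalence between groups". The rule that follows, including a clause left unfinished, is "Significant covariates will be added to adjust for nonequivalence. Or variables related to missing data". Baseline HbA1c is not named, no threshold is given, and the form in which a covariate would enter is not stated. Nothing says how the baseline means are parameterised.

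On timing, protocol section 4 has the Initial Visit at which "baseline self-report and clinical assessments will be performed", and then "At the conclusion of the Initial Visit, the Project Manager will unveil group assignment". Section 7 (Study Schedule) lists the contents of the baseline visit in a different order: "Informed Consent, Randomization, Brief diabetes education session to be delivered, Labs", followed by blood pressure and surveys. Section 4 also states that "DD and DD-Me will be delivered between baseline and month-6 assessments".

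**The concern.** With group, categorical time and their interaction, the default model gives each group a free baseline mean. The interaction terms are then differences in change from baseline. When baseline is measured before assignment is known, randomization makes the true baseline means equal. Estimating them separately adds the noise of chance baseline differences to the treatment contrast.

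The imbalance rule is not a substitute. It makes adjustment depend on the observed data and on a threshold the SAP does not give. It may also do nothing: baseline is itself one of the repeated outcomes, so adding it only as a main effect to a random-intercept model with complete data leaves the interaction estimate and its standard error unchanged.

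What is at stake is efficiency, not bias: wider intervals for HbA1c, LDL-c and SBP, and lower power for the comparison the trial was sized on.

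**Working it through.** **Inputs (SAP, Power and Sample Size).** Stationary AR(1), ρ = .45; α = .05 (two-sided assumed) and power .80; d = .33; 138 per group; missing data 15% per time-point or 30% overall. I read the last as monotone dropout with retention 1, .85 and .70. That reading is an assumption. (The SAP's 0.5/1.3 is .385, not .33; this does not affect the variance ratios.)

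**The plan's own figure.** For the group difference averaged over months 6 and 12, n = 2(1.960 + 0.842)² Σ c_s c_t R_st/√(r_s r_t) / d², with weights c of ½ on each of months 6 and 12, correlations R and retentions r. This gives 135.9, so 136 per group against the stated 138. The SAP does not name its contrast, so the match is not unique. Also 414 × .70 = 290, as stated.

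**Variance of one group's estimated means** (units σ²/n, maximum likelihood under monotone dropout):
- Baseline: 1
- Month 6: .45² + (1 − .45²)/.85 = .2025 + .9382 = 1.1407
- Month 12: .45² × 1.1407 + (1 − .45²)/.70 = .2310 + 1.1393 = 1.3703
- Covariance with baseline: .45 (month 6) and .45² = .2025 (month 12)

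**Free baseline means**, two groups of n:
- Month 6: 2(1 + 1.1407 − 2 × .45) = 2.481
- Month 12: 2(1 + 1.3703 − 2 × .2025) = 3.931

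**Equal baseline means**, two groups of n:
- Month 6: 2(1.1407 − .45²) = 1.876
- Month 12: 2(1.3703 − .2025²) = 2.659

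**Ratios.** 1.876/2.481 = .756 and 2.659/3.931 = .676, so 24.4% and 32.4% of inverse variance is lost. Intervals narrow by 1 − √.756 = 13.0% and 1 − √.676 = 17.8%. The ratios do not depend on allocation or on having two or three groups.

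**Sensitivity** (retention 1/.85/.70 unless stated; the alternative correlations and SDs are assumptions):

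| Scenario | Loss, month 6 | Loss, month 12 |
|---|---|---|
| AR(1) .45, complete data | 27.5% | 39.9% |
| AR(1) .45, 30% missing at both follow-ups | 21.0% | 31.7% |
| AR(1) .60 | 17.5% | 25.7% |
| Exchangeable .45 | 24.4% | 21.3% |
| Exchangeable .60 | 17.5% | 15.2% |
| AR(1) .45, baseline SD 20% smaller | 11.6% | 21.2% |
| AR(1) .45, baseline SD 20% larger | 37.5% | 42.8% |
| Exchangeable .60, baseline SD 20% smaller | 5.0% | 4.3% |

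**Power of the joint 2-df group-by-time test**, AR(1) .45, month-6 effect .33 SD, free versus equal baseline means. Pairwise is 138 v 138; pooled is DD 138 v DD-Me 276.

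| Month-12 effect | Noncentrality, pooled | Loss | Power, pairwise | Power, pooled |
|---|---|---|---|---|
| Same as month 6 | 8.76 v 13.34 | 34% | .63 v .82 | .76 v .92 |
| Halved | 8.35 v 10.70 | 22% | .60 v .72 | .74 v .84 |
| Gone | 11.60 v 12.46 | 7% | .76 v .79 | .87 v .90 |

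**The imbalance rule.** In 200,000 simulated trials (three groups of 138, complete data, AR(1) .45, no true baseline difference), an F-test at p < .05 would bring in baseline in 5.0% of trials, and any pairwise difference of at least 0.2 SD in 22.2%. Both triggers are assumptions. If triggered trials adjust fully and the rest use change from baseline, mean squared error relative to always using change is .946/.921 (p < .05) and .848/.780 (0.2 SD) at months 6/12. Prespecified adjustment gives .725/.601.

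**Main effect only.** In 25 simulated trials under each of AR(1) .45 and exchangeable .45, with a random intercept and complete data, adding baseline as a main effect changed no interaction estimate or standard error. With monotone dropout the mean standard error fell only 4–5%.

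**The case against.** The planned contrast is a standard, valid analysis, so this is an efficiency improvement and not a defect in inference. That stands.

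The size is not fixed, for four reasons.

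- **Missing data.** The 24% and 32% need the dropout reading as well as the correlation. That is true, but complete data give larger losses, so the headline is not inflated.
- **The imbalance rule.** It could recover part of the loss. With a 0.2 SD trigger and full adjustment, the remaining loss with complete data is 1 − .725/.848 = 15% and 1 − .601/.780 = 23%. A 0.1 SD trigger would fire in 68% of trials (ratios .741/.624) and leave only 2% and 4%. This is fair, but recovery rests on a threshold and a model form the SAP does not state.
- **Baseline spread.** Entry requires raised HbA1c, SBP and/or LDL-c, which can narrow baseline spread and shrink the gain. With baseline SD 20% smaller and exchangeable correlation .70 the loss is 1.6% and 1.4%; at .80 it is zero. The constrained model was never less precise, however, and the SAP itself assumes stationarity.
- **Choice of test.** The powers above are for two-group tests, whereas a three-group interaction has 4 df. With both DD-Me arms equally effective, 4-df power goes from .65 to .85 (equal effects), .63 to .75 (halved) and .79 to .82 (gone). The pattern is the same.

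Finally, the Study Schedule is a list and need not imply order, and section 4 already puts assessments first. That is reasonable; confirming the order is a small condition on the fix, not a separate fault.

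**Conclusion.** The point holds. The SAP prespecifies neither baseline adjustment nor equal baseline means for its primary contrast. With free baseline means, that contrast loses about 24% (month 6) and 32% (month 12) of inverse variance. These figures rest on the SAP's AR(1) .45, equal variances, the cumulative 15%/30% dropout reading, and the imbalance rule not bringing in full baseline adjustment. They shrink with higher long-lag correlation or a narrower baseline distribution, and can reach zero.

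The benefit to the joint test depends on the shape of the effect. Because delivery ends at month 6, fading is plausible, so the equal-effects gain (pairwise .63 to .82) is near the upper end. If the effect has gone by month 12 the gain is about 3 points. The planned analysis remains unbiased; the change is worth making because it costs almost nothing.

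**What to change.** Add one sentence to the Analytic Plan: in the same maximum-likelihood model with categorical time, baseline means are set equal across groups whatever imbalance is observed, so that treatment enters only through group-by-month-6 and group-by-month-12 terms. The joint test of those terms can stay as the primary test.

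An alternative is to model months 6 and 12 as outcomes with baseline-by-time as a covariate, testing the group differences at both visits jointly. This is equivalent with complete data and nearly so with dropout.

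Apply the change to HbA1c, LDL-c and SBP. For patient-reported outcomes, first reconcile the order of the baseline visit in protocol section 4 with the Study Schedule, and apply the constraint once it is confirmed that surveys are completed before assignment is unveiled. The same clarification documents the order for blood pressure and labs.

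The cost is one SAP sentence and one protocol clarification, with no new data, participants or software.
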